### **Change #7**

#### **12.3 Defined Daily Dose**

Updated Table 12-1 to include the Compound Perampanel with ATC code =N03AX22 and WHO DDD (mg/day)=8.

REDACTED COPY

This document cannot be used to support any marketing authorization application and any extensions or variations thereof

## 13.3 AMENDMENT 3

### Rationale for the amendment

The SAP has been amended to implement any changes to the planned analyses made during the course of the study since the approval of the previous version of the SAP and to incorporate any clarifications to the text. In particular the SAP was amended to repeat analyses on the modified FAS in order to provide summaries of demography, baseline characteristics, concomitant medications, effectiveness and safety for patients treated according to the approved SmPC during their Observation Period. This will provide an analysis representing the on-label use of BRV.

### Modifications and changes

#### Global changes

Corrections to use “Patient” instead of “Subject” throughout the text, as appropriate, were made, except titles from the SAP template or populations. The UCB style guide indicates to use numbers instead of spelling them out so this change was made throughout the document.

#### Specific changes

##### Change #1

##### List of abbreviations.

The following abbreviation were added

BID	“bis in die”/twice daily
NA	Not applicable

##### Change #2

##### 1 Introduction

##### From:

This SAP is based upon, and assumes familiarity with, the Final Protocol dated 04 Nov 2015.

##### To:

This SAP is based upon, and assumes familiarity with, the Final Protocol Amendment dated 25 Oct 2018.

##### Change #3

##### 2.3 Study design and conduct

##### From:

It is planned to include 430 patients in the study.

**To:**

It is planned to include 530 patients in the study.

**Change #4**

**2.4 Determination of sample size**

**From:**

A sample size of 430 patients was chosen for this study in order to obtain 385 patients in the Full Analysis Set (FAS), which allows for approximately 10% of patients to not be included.

When the sample size is 385, a 2-sided 95% confidence interval (CI) for a single proportion using the large sample normal approximation will extend 0.05 from the observed proportion for an expected proportion of 0.50. As an example, given an observed retention rate of 50%, a sample size of 385 patients would give a 2-sided 95% CI of 45% to 55% based on the large sample normal approximation to the binomial distribution.

It is, therefore, planned to have 430 patients, and withdrawals will not be replaced.

**To:**

Initially, a sample size of 430 patients was chosen for this study in order to obtain 385 patients in the Full Analysis Set (FAS), which allows for approximately 10% of patients to not be included.

When the sample size is 385, a 2-sided 95% confidence interval (CI) for a single proportion using the large sample normal approximation will extend 0.05 from the observed proportion for an expected proportion of 0.50. As an example, given an observed retention rate of 50%, a sample size of 385 patients would give a 2-sided 95% CI of 45% to 55% based on the large sample normal approximation to the binomial distribution.

However, since the first 100 patients were all enrolled at sites in Germany in early 2016 and the enrollment in that country was closed, it was believed that ongoing enrollment in other countries would be following different best practices in BRV usage, which could lead to wide variation in this NIS. For this reason, 100 additional patients are planned to be enrolled to obtain 385 patients in the FAS at non-German sites.

It is, therefore, planned to have 530 patients, and withdrawals will not be replaced.

**Change #5**

**3.2.2 Visit 4, Month 12/Withdrawal Visit**

**From:**

Patients with early study termination (ie, those who complete the Study Termination [Dropout] CRF page), will have their Visit 4 (Month 12/Withdrawal) visits prior to the preferred visit window for Month 12 of greater than 330 days after date of first BRV administration. Patients completing the study (ie, those who complete the Study Termination NIS [Completed Subject] CRF form), will have their Visit 4 (Month 12/Withdrawal) visits within the preferred visit

window for Month 12 of greater than 330 days after date of first BRV administration. Therefore, Visit 4 will be analyzed as follows depending on the objective and variable being analyzed:

- Visit 4 (Month 12): Including only patients who are study completers

...

EpiTrack	No mapping as no scheduled visit	
----------	----------------------------------	--

**To:**

Patients with early study termination (ie, those who complete the Study Termination [Dropout] CRF page), will have their Visit 4 (Month 12/Withdrawal) visits prior to the preferred visit window for Month 12 of greater than or equal to 330 days after date of first BRV administration. Patients completing the study (ie, those who complete the Study Termination NIS [Completed Subject] CRF form), will have their Visit 4 (Month 12/Withdrawal) visits within the preferred visit window for Month 12 of greater than or equal to 330 days after date of first BRV administration. Therefore, Visit 4 will be analyzed as follows depending on the objective and variable being analyzed:

- Visit 4 (Month 12): Including only patients who are study completers with a Visit 4 within the preferred visit window for Month 12 of greater than 330 days after the date of first BRV administration.

...

EpiTrack	No mapping as no scheduled visit	150-210
----------	----------------------------------	---------

## Change #6

### 3.3 Definition of Baseline values

**From:**

In this NIS, Baseline is defined as the data collected at Visit 1. For seizure frequency variables, Baseline is defined in Section 8.2.2.1.

**To:**

In this NIS, Baseline is defined as the data collected at Visit 1. For prior and concomitant medications and for AED drug load, Baseline is defined as first BRV administration. For seizure frequency variables, Baseline is defined in Section 8.2.2.1.

## Change #7

### 3.5 Analysis sets

**From:**

- BRV is administered as an adjuvant therapy, defined as
  - patient receiving at least 1 concomitant AED at Baseline and at each post-Baseline documented visit.

- patient does not have a protocol violation of Selection Criterion # 6

**To:**

- BRV doses were administered in 2 equally divided doses (BID). According to when the first dose or last dose is administered, other administration schemes can occur. Hence any patients receiving BRV not divided into 2 equally doses will be reviewed during the DEM to determine whether they are taking BRV per SmPC.
- BRV is administered as an adjuvant therapy, defined as
  - patient receiving at least 1 concomitant AED at Baseline and at each post-Baseline documented visit.
  - patient does not have a protocol violation of Selection Criterion # 6

Modified FAS listings to investigate compliance with the approved SmPC will be created and reviewed at the DEM prior to database lock in order to determine which patients will be included in the modified FAS. If the number of patients in the modified FAS is sufficiently different to that in the FAS, then key demographic, effectiveness and safety tables will be repeated on the modified FAS.

**Change #8**

**3.8 Coding dictionaries**

**From:**

Adverse drug reactions will be coded using version 18.1 of the Medical Dictionary for Regulatory Activities (MedDRA). Medications will be coded using the September 2015 version of World Health Organization Drug Dictionary (WHODD).

**To:**

Adverse drug reactions will be coded using version 20.0 or higher of the Medical Dictionary for Regulatory Activities (MedDRA). Medications will be coded using the September 2017 version of World Health Organization Drug Dictionary (WHODD).

**Change #9**

**4.3 Interim analyses and data monitoring**

Due to the extension in patient recruitment on the study, there will be an increase in sample size and a third snapshot analysis to take place in 2019. The following paragraph was added:

- A third snapshot analysis will be performed with a data cut-off date on 28 Nov 2019. All TFLs identified in the SAP and Mock TFL shells will be delivered including all visits in the database at the time of the snapshot cut off.

---

## Change #10

### 4.6 Use of subsets of subjects

#### From:

All effectiveness analysis will be performed on the FAS. In addition, to provide an estimate of effectiveness for patients using BRV per the approved SmPC, retention at 12 months will be repeated using the modified FAS.

#### To:

All effectiveness analysis will be performed on the FAS and the modified FAS to an estimate of effectiveness for patients using BRV per the approved SmPC.

## Change #11

### 6 Demographics and other baseline disease characteristics

#### From:

All demography, Baseline disease characteristics, and historical and concomitant medication summaries will be presented on the SS. Demography will be also presented on the All Subjects Documented set. Listings of all data will be presented on the All Subjects Documented set.

#### To:

All demography, Baseline disease characteristics, and historical and concomitant medication summaries will be presented on the SS and modified FAS, except for subgroup analyses that will only be presented on the SS. Demography will be also presented on the All Subjects Documented set. Listings of all data will be presented on the All Subjects Documented set.

## Change #12

### 6.4 Prior and concomitant medications

#### From:

Medications classified as AEDs or non-AEDs in the CRF, will be reviewed during the DEM to ensure correct classification. In addition, historical and concomitant medications will be reviewed to ensure documentation in the correct CRF pages. Historical medications are defined as medications discontinued prior to Visit 1 (Baseline). Concomitant Baseline medications are defined as those being taken on the same day as at study entry (on the same day as Visit 1). Concomitant medications are medications taken at least 1 day in common with the study medication dosing period. In other words, those that started on or prior to the date of first BRV administration, and have an end date on or after the date of first BRV administration or are ongoing; or those starting after the 1st BRV administration and on or before last BRV administration.

Non-AED historical medications, those stopped before Visit 1 (Baseline), should not be collected in the CRF.

As there are snapshot analyses throughout the study and data entry is ongoing, any non-coded terms at the time of reporting will report the WHODD Anatomical Main Group [Level 1], Pharmacological Subgroup [Level 3] and PT as UNCODED in the tables and listings.

The number and percentage of patients with each of the following medication types will be summarized overall and by WHODD Anatomical Main Group [Level 1], Pharmacological Subgroup [Level 3] and PT.

- Number and percentage of patients with AED concomitant medications (including LEV)
- Number and percentage of patients with non-AED concomitant medications

Where necessary, PTs may be collapsed into AED PT categories for study reporting and where applied this will be added as a footnote on the output. In addition, LEV use will be combined with other AED medications and reported in the table of AED concomitant medications.

Patients documented as having used a vagus nerve stimulation (VNS) magnet will be considered as having active use at Visit 1 (Baseline) and during the study. Hence, VNS use is counted as an AED for AEDs taken at study entry. As historical AEDs are defined as medications discontinued prior to Visit 1 (Baseline), VNS use at Visit 1 will not be counted as a historical AED. Lifetime AEDs are defined as a sum of the historical AEDs and AEDs taken at study entry. As LEV can be included in both historical AEDs and AEDs at study entry, it will only be counted once in the calculation of Lifetime AEDs.

**To:**

Medications classified as AEDs or non-AEDs in the CRF, will be reviewed during the DEM to ensure correct classification. In addition, historical and concomitant medications will be reviewed to ensure documentation in the correct CRF pages. Historical medications are defined as medications discontinued prior to the date of first BRV administration. Medications at study entry are defined as those being taken on the same day as first BRV administration.

Concomitant medications are medications taken at least 1 day in common with the study medication dosing period. In other words, those that started on or prior to the date of first BRV administration, and have an end date on or after the date of first BRV administration or are ongoing; or those starting after the first BRV administration and on or before last BRV administration.

Non-AED historical medications, those stopped before the date of first BRV administration, should not be collected in the CRF.

As there are snapshot analyses throughout the study and data entry is ongoing, any non-coded terms at the time of reporting will report the WHODD Anatomical Main Group [Level 1], Pharmacological Subgroup [Level 3] and PT as UNCODED in the tables and listings.

The number and percentage of patients with each of the following medication types will be summarized overall and by WHODD Anatomical Main Group [Level 1], Pharmacological Subgroup [Level 3] and PT.

- Number and percentage of patients with AED concomitant medications (including LEV)
- Number and percentage of patients with non-AED concomitant medications

Where necessary, PTs may be collapsed into AED PT categories for study reporting and where applied this will be added as a footnote on the output. In addition, LEV use will be combined with other AED medications and reported in the table of AED concomitant medications.

Patients documented as having used a vagus nerve stimulation (VNS) magnet will be considered as having active use on the date of first BRV administration and during the study. Hence, VNS use is counted as an AED for AEDs taken at study entry. As historical AEDs are defined as medications discontinued prior to the date of first BRV administration, VNS use at study entry will not be counted as a historical AED. Lifetime AEDs are defined as a sum of the historical AEDs and AEDs taken at study entry. As LEV can be included in both historical AEDs and AEDs at study entry, it will only be counted once in the calculation of Lifetime AEDs.

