## 8.2 Withdrawal criteria

Patients are free to withdraw from the NIS at any time, without prejudice to their continued care.

Physicians are free to add or withdraw any medication or to withdraw the patient from the study at their own discretion.

If the physician elects to permanently stop BRV treatment, the patient will be withdrawn from the study.

The primary reason for withdrawal from the NIS must be documented in the patient's eCRF. When the primary reason for withdrawal is lack of effectiveness or an AE, both must be reported as described in [Section 10.1.8](#) of the protocol.

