### **6.4 Prior and concomitant medications**

Medications will be reviewed during the DEM to ensure correct classification. In addition, historical and concomitant medications will be reviewed to ensure documentation in the correct CRF pages. Historical medications are defined as medications discontinued prior to the date of first BRV administration. Medications at study entry are defined as those being taken on the same day as first BRV administration. Concomitant medications are medications taken at least 1 day in common with the study medication dosing period. In other words, those that started on or prior to the date of first BRV administration, and have an end date on or after the date of first BRV administration or are ongoing; or those starting after the first BRV administration and on or before last BRV administration.

Non-AED historical medications, those stopped before the date of first BRV administration, should not be collected in the CRF.

As there are snapshot analyses throughout the study and data entry is ongoing, any non-coded terms at the time of reporting will report the WHODD Anatomical Main Group [Level 1], Pharmacological Subgroup [Level 3] and PT as UNCODED in the tables and listings.

The number and percentage of patients with each of the following medication types will be summarized overall and by WHODD Anatomical Main Group [Level 1], Pharmacological Subgroup [Level 3] and PT.

- Number and percentage of patients with AED concomitant medications (including LEV)
- Number and percentage of patients with non-AED concomitant medications

Where necessary, PTs may be collapsed into AED PT categories for study reporting and where applied this will be added as a footnote on the output. In addition, LEV use will be combined with other AED medications and reported in the table of AED concomitant medications.

Patients documented as having used a vagus nerve stimulation (VNS) magnet will be considered as having active use on the date of first BRV administration and during the study. Hence, VNS use is counted as an AED for AEDs taken at study entry. As historical AEDs are defined as medications discontinued prior to the date of first BRV administration, VNS use at study entry will not be counted as a historical AED. Lifetime AEDs are defined as a sum of the historical AEDs and AEDs taken at study entry. As LEV can be included in both historical AEDs and AEDs at study entry, it will only be counted once in the calculation of Lifetime AEDs.

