### **8.3.4 Change in drug load of AEDs**

Drug load of AEDs will be calculated at first BRV administration, Visit 4 (Month 12), and Visit 4 (Month 12/Withdrawal). Drug load of AEDs will include all concomitant AEDs and LEV (recorded separately in the CRF), in addition to BRV dosing.

Only AEDs (recorded as an AED, as LEV, or as BRV dosing) that are being taken on the date of the visit will be included in the calculations. Partial dates will be imputed as described in [Section 4.2.2](#) to ensure the inclusion of any medications which have the potential to have been taken on the date of the visit.

Drug load per AED at the visit is calculated as: daily dose (mg) / DDD, where DDD for each AED is defined in [Section 12.3](#) and daily dose for each AED is calculated as follows:

1. Convert the dose per intake into mg using the unit recorded for each AED in the CRF (ie, 1g = 1000mg)
2. Using the frequency of dose recorded, multiply the dose per intake in mg by the values shown in [Table 8-4](#).

Table 8-4: Daily dose calculation		
Frequency	Description	Multiply dose per intake by:
QD	Once daily	1
BID	Twice daily	2
TID	3 times daily	3
QID	4 times daily	4
5XD	5 times daily	5
6XD	6 times daily	6
QOD	Every other day	1/2
QAM	Every morning	1
QPM	Every evening	1
QS	Every week	1/7
Q2S	Every 2 weeks	1/14
BIS	Twice per week	2/7
TIS	3 times per week	3/7
QM	Every month	1/28
BIM	Twice per month	2/28
TIM	3 times per month	3/28
Q2M	Every 2 months	1/56
Q3M	Every 3 months	1/84
PRN	As needed	Excluded from calculation

The drug load per AED at each visit will be added together to give a total AED drug load per visit. To avoid an underestimation of the drug load on the first and last visits (on which only 1 of the usual 2 doses may have been recorded), AED drug load at first BRV administration will be

calculated for the Day 2 for all patients and the last available record with morning and evening dosage will be used for the Visit 4 drug load analysis.

All drug load analyses will be performed on the FAS and the modified FAS.

The total AED drug load at first BRV administration (Baseline), Visit 4 (Month 12), and Visit 4 (Month 12/Withdrawal), and the change from Baseline will be summarized by descriptive statistics. Change from Baseline is defined as: Total AED drug load at Visit 4 (Month 12) or Visit 4 (Month 12/Withdrawal) – total AED drug load at first BRV administration (Baseline).

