The number of AEDs (including LEV, VNS use and BRV) taken per patient at first BRV administration (Baseline), Visit 4 (Month 12), and Visit 4 (Month 12/Withdrawal), and change from Baseline will be summarized by descriptive statistics. The number of AEDs at first BRV administration (Baseline) will be equal to the number of AEDs at Study Entry as described in [Section 6.4](#). Patients with VNS use at first BRV administration (Baseline) will be considered to have VNS use during the entire study and as such it will be counted as an AED at Visit 4 (Month 12) and Visit 4 (Month 12/Withdrawal) as appropriate. The total number of AEDs at a visit is a count of the number of concomitant AEDs, LEV, or BRV that are being taken on the date of the visit with partial dates imputed as described in Section 4.2.2, plus any VNS use. Change from Baseline is defined as: Total number of AEDs at Visit 4 (Month 12) or Visit 4 (Month 12/Withdrawal) – total number of AEDs at first BRV administration (Baseline).

A by-patient listing of drug load data will be provided on the All Subjects Documented set. The listing will include the total drug load, number of AEDs (including LEV and BRV) taken per patient, the changes from Baseline, AEDs taken (including LEV or BRV), the daily dose per given product, DDD, drug load per AED, and frequency at each visit.

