## Change #22

### 8.3.4 Change in drug load of AEDs

#### From:

The total AED drug load at Visit 1 (Baseline), Visit 4 (Month 12), and Visit 4 (Month 12/Withdrawal), and the change from Baseline will be summarized by descriptive statistics on the FAS. Change from Baseline is defined as: Total AED drug load at Visit 4 (Month 12) or Visit 4 (Month 12/Withdrawal) – total AED drug load at Visit 1 (Baseline).

The number of AEDs (including LEV, VNS use and BRV) taken per patient at Visit 1 (Baseline), Visit 4 (Month 12), and Visit 4 (Month 12/Withdrawal), and change from Baseline will be summarized by descriptive statistics on the FAS. The number of AEDs at Visit 1 (Baseline) will be equal to the number of AEDs at Study Entry as described in [Section 6.4](#). Patients with VNS use at Visit 1 (Baseline) will be considered to have VNS use during the entire study and as such it will be counted as an AED at Visit 4 (Month 12) and Visit 4 (Month 12/Withdrawal) as appropriate. The total number of AEDs at a visit is a count of the number of concomitant AEDs, LEV, or BRV that are being taken on the date of the visit with partial dates imputed as described in [Section 4.2.2](#), plus any VNS use. Change from Baseline is defined as: Total number of AEDs at Visit 4 (Month 12) or Visit 4 (Month 12/Withdrawal) – total number of AEDs at Visit 1 (Baseline).

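### As written, the SAP leaves out of the Visit 4 (Month 12/Withdrawal) drug load and AED count any non-levetiracetam AED first started after the last brivaracetam dose

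*SAP*

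**What the plan says.** **Definition.** SAP 6.4 gives the general rule: "Concomitant medications are medications taken at least 1 day in common with the study medication dosing period". It then spells the rule out. A drug begun after the first BRV dose qualifies only as one of "or those starting after the first BRV administration and on or before last BRV administration". These words are in the current 6.4 as well as in the log for SAP Amendment 3. The SAP has no other definition of the term.

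**Use at Visit 4.** SAP 8.3.4 builds the load as follows: "Drug load of AEDs will include all concomitant AEDs and LEV (recorded separately in the CRF), in addition to BRV dosing". The next sentence limits this to "Only AEDs (recorded as an AED, as LEV, or as BRV dosing) that are being taken on the date of the visit". For the number of AEDs it says: "The total number of AEDs at a visit is a count of the number of concomitant AEDs, LEV, or BRV", again limited to those in use on the visit date, plus VNS.

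**Two further rules in 8.3.4.** For the load, "the last available record with morning and evening dosage will be used for the Visit 4 drug load analysis". For the count, Baseline is said to include BRV but is also set equal to the AEDs at study entry from 6.4. SAP 4.8 and 6.4 give that variable a category of 0.

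**Who is concerned.** Protocol 8.2 states: "If the physician elects to permanently stop BRV treatment, the patient will be withdrawn from the study". Protocol 5 and Table 17-1 then ask for Visit 4 data as a Withdrawal Visit, and Table 17-1 has AED changes after Visit 1 recorded. Under SAP 3.2.2, Visit 4 (Month 12/Withdrawal) includes these patients and Visit 4 (Month 12) is limited to completers.

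**The concern.** A definition tied to the BRV dosing period suits a table of concomitant medication. It does not suit a variable meant to describe what the patient takes at the end of observation, because BRV may already have stopped by then. The replacement drug is in the database and in use at the visit, yet it fails the overlap test. LEV is named separately and escapes that test, so two otherwise identical switches are scored differently.

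This also works against 8.3.4's own purpose. That section imputes partial dates so that any drug possibly in use on the visit date is included.

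Change in AED drug load to the end of the Observation Period is a protocol variable (Protocol 4.3). The Month 12/Withdrawal summary is the one that covers patients who left early, and they are the patients most likely to have been switched.

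**Working it through.** The plan states no figure that depends on this rule, so there is nothing to reproduce. The check applies 6.4 and 8.3.4 to a hypothetical patient.

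**Inputs.** The DDDs are from SAP Table 12-1: carbamazepine 1000 mg, BRV 100 mg, lacosamide 300 mg, LEV 1500 mg. Assumptions: each drug is taken at exactly 1 DDD, carbamazepine continues throughout, and the last BRV dose is on Day 150. Doses and days are illustrative only.

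Baseline load = 1000/1000 + 100/100 = 2.0.

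**Load at Visit 4, using only drugs in use on the visit date**

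| Replacement and start | Visit day | Concomitant under 6.4? | Load as written (change) | Load with all AEDs in use (change) | Error |
|---|---|---|---|---|---|
| Lacosamide, Day 140 | 165 | Yes | 2.0 (0) | 2.0 (0) | 0 |
| Lacosamide, Day 150 | 165 | Yes | 2.0 (0) | 2.0 (0) | 0 |
| Lacosamide, Day 151 or 160 | 165 | No | 1.0 (-1.0) | 2.0 (0) | -1.0 |
| LEV, Day 151 | 165 | Listed separately | 2.0 (0) | 2.0 (0) | 0 |
| Lacosamide, Day 151 | 150 | Not yet started; BRV still taken | 2.0 (0) | 2.0 (0) | 0 |

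Only a non-LEV drug started strictly after the last BRV dose and on or before the visit is lost. The shortfall is the replacement's dose/DDD, here 300/300 = 1.0.

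**Effect of the Visit 4 dose-record rule on the load (lacosamide from Day 151, visit Day 165).** If that rule brings back the last BRV record:
- as written: carbamazepine 1 + BRV 1 = 2.0, change 0, so no fall appears;
- with lacosamide added but the record rule unchanged: 1 + 1 + 1 = 3.0, change +1.0, a false rise.

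**Number of AEDs, same patient.** Visit 4 count as written = 1; counting all AEDs in use = 2.
- Baseline includes BRV (2): the reported change is 1 - 2 = -1, against 2 - 2 = 0. This is a false fall.
- Baseline excludes BRV (1): the reported change is 1 - 1 = 0, against 2 - 1 = +1. This is a hidden rise.

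The error is -1 in both cases; only its appearance differs.

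**Mean error in the Month 12/Withdrawal summary.** Let w be the share of patients in the summary who withdrew. Let s be the share of those with a non-LEV AED first started after the last BRV dose and in use at the visit. Per 1 DDD or 1 AED:

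mean error = -(w x s)

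| w (assumed) | s = 10% | s = 50% | s = 100% |
|---|---|---|---|
| 10% | -0.01 | -0.05 | -0.10 |
| 30% | -0.03 | -0.15 | -0.30 |
| 50% | -0.05 | -0.25 | -0.50 |

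For the load, this formula assumes that stopped BRV is not brought back.

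**The case against.** The best defence is that *concomitant AEDs* in 8.3.4 names a CRF source and not the 6.4 time window. There is support for this:
- The term sits beside LEV and BRV as one of three record types.
- 6.4 places LEV inside concomitant AEDs while 8.3.4 lists it apart, so the two sections do not use the term identically.
- Protocol Table 17-1 uses the same label for what is collected at Visit 4, with no cut-off at the last BRV dose.
- 8.3.4 cites 6.4 only for the study-entry count.
- The stated aim of the date imputation favours inclusion.

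This reading is possible for the load. It is weak for the count, whose definition attaches the term directly to the drugs in use at the visit. In the load paragraph, the following sentence opens with a restriction and so cannot widen the set. A programmer applying the only definition in the SAP would drop the drug.

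Two further objections stand and limit the point. First, the documents do not say when the Withdrawal Visit falls relative to the last BRV dose. If the stop is decided at that visit, nothing is lost. Second, drug load is one of the *other* variables in a descriptive study, and the primary variable, retention, is untouched.

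A reader might go further and infer that patients who stop BRV will generally show a false fall in both measures, always in one direction, with a mean error of 0.125 to 0.25 at 50% retention. The documents do not support this. Overlapping and same-day switches are counted. The dose-record rule may mask the fall in load or turn it into a rise. The Baseline count may exclude BRV. The proportion of 0.50 in SAP 2.4 is a value for planning interval width, and non-retention under SAP 8.1.1 also includes study termination for other reasons. The 0.125 to 0.25 further requires that 25% to 50% of those who stop BRV start such a drug, a share found nowhere in the documents.

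**Conclusion.** The point holds within narrow limits. Followed as written, SAP 6.4 and 8.3.4 together drop a recorded non-LEV AED that was first started after the last BRV dose and is in use at the withdrawal visit. For each such patient the Visit 4 count is 1 too low and the load is too low by the replacement's dose/DDD.

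Switches that overlap BRV or occur on its last day, and withdrawal visits held while BRV is still taken, are unaffected. So, in essence, is the completers-only Visit 4 (Month 12) summary, because a permanent stop of BRV leads to withdrawal. That a switch to LEV is counted assumes that its separate listing in 8.3.4 exempts it from the overlap test.

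The omission always lowers the Visit 4 value, but how the reported change looks is not settled. For the count it depends on whether Baseline includes BRV, which the SAP leaves contradictory. For the load it depends on whether the dose-record rule carries stopped BRV forward. The size is unknown: -0.01 to -0.50 per 1 DDD or 1 AED is a range over assumed shares, not an estimate. The correction should be made because it is cheap and the present rule can misstate treatment in patients who left BRV.

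**What to change.** Amend SAP 8.3.4 in one edit:

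1. For both drug load and number of AEDs, count every AED recorded in the CRF, including LEV and BRV, that is in use on the Visit 4 date, whether or not it overlaps BRV dosing. Keep the 6.4 definition for the concomitant medication tables.
2. State that the Visit 4 dose-record rule does not carry forward BRV that was stopped before the visit. Without this, item 1 alone could count both BRV and its replacement.
3. Make the Baseline and Visit 4 AED counts treat BRV the same way, and reconcile this with the study-entry variable and its category of 0.

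The cost is a few phrases in the SAP and a change to the programming filter. No new data are needed, since AED changes after Visit 1 are already recorded.
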